## **9.6 Vital Signs**

### **9.6.1 Variables**

The following vital signs will be summarized.

- Weight
- Systolic blood pressure (mmHg)
- Diastolic blood pressure (mmHg)

### **9.6.2 Analysis**

Subject incidence of clinically meaningful changes since baseline for weight and blood pressure will be presented for the Safety and O-Safety populations as shown below:

- Proportion of subjects with weight loss  $\geq 10\%$  after first dose
- Subjects with at least 2 post-baseline assessments and who got worse since baseline and met the following blood pressure criteria on 2 or more visits (need not be consecutive) after first dose (JNC criteria were modified to include single measurement per time point when triplicate assessments were unavailable; JAMA 2003;289:2560):
  - Pre-hypertension: SBP 120-139 mmHg or DBP 80-89 mmHg
  - Stage 1: SBP 140-159 mmHg or DBP 90-99 mmHg
  - Stage 2: (SBP  $\geq 160$  mmHg and DBP  $< 120$ ) or DBP 100-119 mmHg
  - Stage 3: DBP  $\geq 120$  mmHg

Only results with assessment dates through the end of the safety observation period (see Section 4.6) will be considered for the summaries.

## **9.7 ECOG Performance Status**

For the purpose of evaluating safety, ECOG will be summarized as shift from baseline tables for, at minimum, the worst value recorded after the initiation of study treatment. Only results with assessment dates through the end of the safety observation period (see Section 4.6) will be tabulated in summary tables for the Safety and O-Safety populations.

Frequencies of ECOG worsening of  $\geq +1$  and  $+2$  change from baseline to worst value after first dose will also be summarized.

## **9.8 Electrocardiogram (ECG)**

Only results with assessment dates through the end of the safety observation period (see Section 4.6) will be considered for summaries. The following categorical summaries will be presented for the Safety and O-Safety populations:

- Number of subjects with triplicate average QTc > 500 ms after first dose per investigator
- Number of subjects with change from baseline in QTc > 60 ms after first dose per investigator

For the above summaries, the most-recent average value from triplicate measurements taken before first dose will be used as baseline. If no triplicate measurements were taken before first dose, the most-recent single value taken before first dose will be used as baseline.

## **9.9 IMPACT OF COVID-19 PANDEMIC**

Summaries and analyses to describe and/or assess the impact of the COVID-19 pandemic will be included in a future amendment to this plan. These may include tabulations of COVID-19 related protocol deviations and patterns of missing data, summaries of COVID-19 AEs, the addition of a per-protocol population, and comparative analyses of selected endpoint before, during and after the pandemic.

## **10 IDENTIFICATION AND SUMMARY OF PROTOCOL DEVIATIONS**

Important protocol deviations as pre-specified in the study Protocol Deviation Management Plan. In accordance with ICH E3, Important eligibility deviations (as documented on study CRFs and Important post-randomization protocol deviations tracked in the study clinical trial management system (CTMS) will be identified and listed separately by study center and subject. Important deviations will be summarized for the OITT and ITT populations by

deviation code (a standardized description e.g. “did not satisfy eligibility criteria” or “received prohibited medication”)

## **11 DATA QUALITY ASSURANCE**

The Clinical, Data Management, Biostatistics, and Medical Writing departments at Exelixis and designees will work diligently and collaboratively to ensure that the data collected and analyzed for this study are of the highest quality. In addition to electronic evaluation of the data and verification of data from source documents at the respective sites, a data review meeting will be held to review the data and correct significant data anomalies before the study database is locked or data are extracted for the purpose of analysis.

## **Appendix A: Date Imputation Rules**

### Incomplete Cancer Diagnosis Date

If *year* is missing (or completely missing): do not impute

If only *day* is missing: set to 15th of the month.

If *day* and *month* are missing: set to July 1st.

If either imputation rule above results in a diagnosis date > informed consent:  
set diagnosis date to the date of informed consent - 1.

### Incomplete Adverse Event Onset Date

Assumption: For on-study Adverse Events.

If *year* is missing (or completely missing): set to the date of first dose.

If (*year* is present and *month* and *day* are missing) or (*year* and *day* are present and *month* is missing):

If *year* = year of first dose: set the date to the first dose date.

If *year* < year of first dose: set *month* and *day* to December 31st.

If *year* > year of first dose: set *month* and *day* to January 1st.

If *month* and *year* are present and *day* is missing:

If *year* = year of first dose, and:

If *month* = month of first dose: set *day* to day of first dose.

If *month* < month of first dose: set *day* to last day of *month*.

If *month* > month of first dose: set *day* to 1st day of *month*.

If *year* < year of first dose: set *day* to last day of month.

If *year* > year of first dose: set *day* to 1st day of month.

For all other cases: set to date of first dose.

### Incomplete Concomitant Medication Start Date

If *year* is missing (or completely missing): do not impute.

If (*year* is present and *month* and *day* are missing) or (*year* and *day* are present and *month* is missing):

Set *month* and day to January 1st.

If *year* and *month* are present and *day* is missing:

Set *day* to 1st day of month.

#### Incomplete Concomitant Medication End Date

If *year* is missing (or completely missing): do not impute.

If (*year* is present and *month* and *day* are missing) or (*year* and *day* are present and *month* is missing):

Set *month* and *day* to December 31st.

If *year* and *month* are present and *day* is missing:

Set *day* to last day of the month.

#### Incomplete Subsequent Anticancer Therapy Start Date

Assumption: Anticancer therapies reported on the Subsequent Anticancer Therapy CRF.

If *year* is missing (or completely missing): set to date decision to discontinue study treatment + 1

If (*year* is present and *month* and *day* are missing) or (*year* and *day* are present and *month* is missing):

If *year* > year of the last dose: Set *month* and *day* to January 1st.

If *year* = year of the last dose: Set *month* and *day* to date of decision to discontinue study treatment + 1

If *year* and *month* are present and *day* is missing:

Set *day* to 1st day of month if the resulting imputed date is greater than date of decision to discontinue study treatment or if the month is before the month of date of decision to discontinue study treatment and year is same or before the year of the date of decision to discontinue study treatment. Otherwise set the imputed date to date of decision to discontinue study treatment + 1

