#### **3.6.1 Treatment Discontinuation**

Subjects will receive study treatment until treatment discontinuation for any of the reasons listed below. Subjects may discontinue study treatment at any time without prejudice. If a subject discontinues study treatment, the reason will be documented in source documents. However, the subject will continue to be followed for safety as described in Section 5.4.1 and survival as described in Section 5.4.2; for subjects who discontinue study treatment prior to radiographic PD, tumor assessments and HRQOL assessments should continue per the protocol-defined schedule (Section 5.4.2). For subjects who discontinue study treatment, every effort must be made to continue protocol-specified evaluations and follow-up (Appendix A; Appendix B) unless the subject also withdraws consent to participate in other study interventions and/or non-interventional study assessments (see Sections 3.6.2 and 12.2). Subjects who request to discontinue study interventions may consent to allow non-interventional study assessments (eg, medical record review and survival contacts) where permitted by local regulations. Otherwise, all subjects will be followed until death or until a decision by the Sponsor is made to stop collection of these data.

The following are possible reasons for discontinuation from study treatment:

- Subject no longer experiences clinical benefit as determined by the investigator (ie, radiographic PD; clinical deterioration attributable to PD and unlikely to reverse with continued study treatment and/or supportive care). Note: If study treatment is withdrawn for this reason, the date of this decision is to be recorded and every effort should be made to continue safety evaluations and collection of nonprotocol treatment information and follow-up information for survival.
- Unacceptable side effects the investigator feels may be due to study treatment
- The investigator feels it is not in the best interest of the subject to continue on study
- Participation in another clinical study using an investigational agent or investigational medical device
- Necessity for treatment with nonprotocol systemic anticancer therapy
- Necessity for withholding study treatment for greater than 8 weeks for AEs, unless continuation of treatment is approved by the Sponsor
- Refusal of sexually active fertile subjects (excluding subjects who have been sterilized) to use medically accepted methods of contraception
- Pregnancy of a female subject

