#### 8.1.2.4 Primary Definition

For the primary analysis directed toward the primary estimand, duration of PFS is defined as the time from randomization to the earlier of either the date of radiographic progression per BIRC or the date of death due to any cause.

$$\text{PFS (months)} = (\text{earliest date of progression, death, censoring} - \text{date of randomization} + 1) / 30.4375$$

General censoring rules for the primary analysis of PFS are described below, with details provided in Table 8(analysis ID PFS-EP-1):

- Subjects who receive systemic NPACT, or local NPACT for disease under study, or non-protocol radiation therapy for disease under study (other than to bone) or surgery to resect target lesions before experiencing an event will be right censored at the date of the last ATA on or prior to the date of initiation of subsequent therapy/surgery. If there is no such tumor assessment after randomization, the subject will be right censored on the date of randomization.
- Subjects who have not experienced an event (and are not otherwise censored) at the time of data cutoff will be right censored on the date of their last tumor assessment after randomization that is on or prior to the data cutoff. If there is no such tumor assessment after randomization, the subject will be right censored on the date of randomization.
- Subjects who miss two or more ATAs (operationally defined as an interval of 126 days in the first year and 196 days after the first year without an ATA) followed by an event (progression or death) will be right censored on the date of their most-recent ATA prior to the missing assessments. If there is no such tumor assessment after randomization, the subject will be right censored on the date of randomization.

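### The partial-date rule for subsequent anticancer therapy (SAP Appendix A) tests month and year separately and mixes last-dose and decision dates, so some imputed starts contradict the record and can change a primary PFS outcome

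*Combined protocol and SAP*

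**What the plan says.** SAP 4.5 refers partial dates to Appendix A. There, the rule headed Incomplete Subsequent Anticancer Therapy Start Date has three parts.

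- **Year missing:** the day after the decision to discontinue study treatment (decision + 1).
- **Month missing, year known:** the recorded year is compared with the year of the last dose. If it is later, the rule is "year of the last dose: Set *month* and *day* to January 1". If it is equal, month and day are set to decision + 1. No other case is listed.
- **Day missing, month and year known:** there are two conditions and a default. The first condition compares full dates: the 1st of the recorded month is used when it falls after the decision. The second keeps the 1st of an earlier month "if the month is before the month of date of decision to discontinue study treatment and year is same or before the year" that contains the decision. When neither condition is met, the default applies: "Otherwise set the imputed date to date of decision to discontinue study treatment + 1".

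The date feeds the primary endpoint. Under SAP 8.1.2.4, a subject who starts systemic non-protocol anticancer therapy (NPACT), or local NPACT for the disease under study, before an event is "right censored at the date of the last ATA on or prior to the date of initiation of subsequent therapy/surgery", where ATA means adequate tumor assessment. Table 8 repeats this for PFS-EP-1.

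Last dose and decision need not be close. Protocol 6.5.1 allows interruptions of up to 8 weeks, and Protocol 3.6.1 lists "Necessity for withholding study treatment for greater than 8 weeks for AEs" among the reasons to discontinue.

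**The concern.** An imputation rule should stay inside what was recorded and give one answer for every input. This one does neither in some cases.

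The second day-missing condition tries to recognise a therapy that began before the decision, but it does so with two separate comparisons. An earlier year combined with an equal or later month number fails the month test and drops to the default. The month-missing part tests one date and assigns from another, which matters whenever last dose and decision fall in different calendar years.

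At stake is whether a subject counts as a PFS event or is censored at an earlier scan. The same start date also bounds best overall response (SAP 8.1.1.1) and enters the alternative PFS estimands, PFS2, the OS sensitivity analysis and time to first systemic NPACT.

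**Working it through.** The plan states no figure to reproduce. The check applies the rule exactly as written. All example dates are illustrative assumptions.

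**Day missing.** Let the recorded month and year be (m, y) and the decision date D. The rule gives the 1st of (m, y) if that date is after D, or if m < month(D) and y ≤ year(D). Otherwise it gives D + 1.

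With D = 10 Feb 2020:

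| Recorded | 1st after D? | m < 2? | y ≤ 2020? | Result |
|---|---|---|---|---|
| Jan 2020 | no | yes | yes | 1 Jan 2020 |
| Dec 2019 | no | no | yes | 11 Feb 2020 |
| Nov 2019 | no | no | yes | 11 Feb 2020 |

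The therapies recorded as starting earlier are dated later. For a therapy recorded in the previous year, the default applies whenever m ≥ month(D). Over 12 × 12 = 144 month pairs that is 12 + 11 + … + 1 = 78. Earlier months in the same year as the decision are always kept.

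Running the rule over every decision date in 2020 (366 dates) gives the share of starts moved out of the recorded month:

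| True start relative to decision | Date pairs | Moved out | Share |
|---|---|---|---|
| 1–365 days after | 133,590 | 0 | 0% |
| 1–30 days before | 10,980 | 819 | 7% |
| 1–90 days before | 32,940 | 4,449 | 14% |
| 1–365 days before | 133,590 | 67,149 | 50% |

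The moved starts become 2 to 366 days later than the true start. In each of the last three rows, 354 pairs are a month-end edge case: the decision is on the last day of the recorded month, so D + 1 falls in the next month. The shares are conditional on the therapy having begun before the decision and on the day being missing.

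**Month missing.** Take last dose 20 Dec 2019 and decision 15 Jan 2020.

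- Recorded 2020: 2020 > 2019, so the result is 1 Jan 2020, which is 14 days before the decision. With the year also missing it would have been 16 Jan 2020.
- Recorded 2019: equal to the last-dose year, so month and day come from 16 Jan 2020. Read as the full date, this is 16 Jan 2020, in the wrong year. Read as month and day only, it is 16 Jan 2019, about 11 months before the last dose. The text supports either reading.
- Recorded 2019 with last dose 20 Jan 2020: no branch applies.

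**Effect on primary PFS.** Take randomization on 1 Jul 2019, with ATAs on 26 Aug, 21 Oct and 16 Dec 2019, and BIRC progression found on an additional scan. SAP 8.1.2.4 gives PFS = (date − randomization + 1)/30.4375.

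- *Example 1.* Therapy recorded Nov 2019, BIRC progression 15 Jan 2020, decision 10 Feb 2020. The rule dates therapy 11 Feb 2020, so progression counts: event at 199/30.4375 = 6.5 months. Respecting the recorded month, therapy is 1 Nov 2019: censored on 21 Oct 2019 at 113/30.4375 = 3.7 months.
- *Example 2.* Therapy recorded 2020, last dose 20 Dec 2019, BIRC progression 8 Jan 2020, decision 15 Jan 2020. The rule dates therapy 1 Jan 2020: censored on 16 Dec 2019 at 169/30.4375 = 5.6 months. Anchored to the decision, therapy is 16 Jan 2020: event at 192/30.4375 = 6.3 months.

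The error can therefore go in either direction.

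**The case against.** **The expected sequence is safe.** Protocol 7.1.2 prohibits systemic NPACT until study treatment has permanently stopped, so a systemic start before the decision is normally a protocol deviation. For starts after the decision with only the day missing, no date leaves its recorded month. This stands and keeps the reach narrow. It is not a full answer: the same section only advises against local treatment and foresees unavoidable cases, and the rule itself contains a clause for months before the decision. The month-missing fault needs no deviation.

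**1 Jan 2020 for a therapy recorded as 2020 is not impossible.** It has the right year and follows the last dose. That is correct. The fault is inconsistency: knowing the year moves the start to before the decision, whereas knowing nothing puts it after.

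**Sensitivity analyses cover this.** PFS-EA2-1 counts systemic NPACT as an event, and PFS-EP-12 and PFS-EP-14 reclassify subjects censored for it. These address informative censoring, but they use the same imputed date, and the last two leave untouched a subject wrongly counted as an event.

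**Stronger readings that the documents do not support.** A reader might infer that the rule ignores the year. It does not: the quoted condition includes a year test, and the other day-missing condition compares full dates. A reader might also infer that using the 1st of the month, when BIRC progression falls later in that month, wrongly deletes events, mainly on cabozantinib. First-of-month is the convention used elsewhere in Appendix A. If therapy did precede progression, censoring is what SAP 8.1.2.4 intends. If the decision came after progression in that month, the rule gives decision + 1 and keeps the event. Nothing in the documents shows a skew by arm.

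**Conclusion.** The rule is wrong as written in three respects. It overrides a known month and year when an earlier-year therapy has a month number equal to or later than the decision month. In the month-missing part it tests the last-dose year but assigns from the decision date. It has no result for a year before the last-dose year. Each of the first two can change a primary PFS outcome if BIRC progression lies between the imputed and the true start.

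The practical size is unknown and probably very small. The first fault needs a missing day and a therapy that began before the decision with New Year between them. The second needs a missing month and last dose and decision in different years. The documents give no frequency of partial therapy dates, so any count of lost or gained events would rest on assumed rates. One affected subject is 1/193, about 0.5% of the planned events. The case for change is that a stated rule for the primary endpoint is faulty and cheap to correct, not that the PFS result is in danger.

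**What to change.** Replace the rule with a comparison of full dates against one anchor, the decision date.

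1. Define the recorded period: the known month, or the known year if the month is missing.
2. If the whole period lies before the decision date, use its first day on or after randomization. This also covers a year before the anchor year.
3. Otherwise use the later of the period's first day and decision + 1.
4. Never leave the recorded period. If decision + 1 falls outside it, use the period's last day.
5. Keep decision + 1 when the year is missing.

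Nov 2019 with decision 10 Feb 2020 then becomes 1 Nov 2019, and 2020 with decision 15 Jan 2020 becomes 16 Jan 2020. Results for day-missing starts after the decision do not change.

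Do not tie the imputed date to the BIRC progression date. That would make a censoring variable depend on the endpoint, and for a year-only record it could move a therapy start by many months.

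The cost is a few lines of SAP text and code, and SAP 4.9 already provides for minor corrections by addendum before unblinding. One drawback remains: for a year-only record wholly before the decision, step 2 is crude. A therapy recorded as 2019 in a subject randomized on 1 Jul 2019 would be dated 1 Jul 2019, possibly months early. Such records should be queried with the site first.

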#### Incomplete Death Date

Identify date of last known alive (LA) prior to death from the following:

- Date of decision to discontinue study treatment from End of Treatment CRF
- Date of last radiographic assessment from End of Radiographic Follow Up CRF
- Date last known alive from Survival Follow Up CRF
- Date of last lab assessment from the Labs dataset

If *year* is missing (or completely missing): set to date of LA + 1

If only *day* is missing: set to the maximum of the first of month or LA + 1

If *month* and *day* are missing:

If *year* of LA = year of death

Set death date to date of LA + 1

If *year* of most-recent contact < year of death

Set *month* and *day* to Jan 1st.

### Incomplete Study Treatment Start Date

Define previous sequential dosing “milestone” as the latest of previous dose stop date, previous dose hold stop date, date of first dose or randomization date.

If *year* is missing (or completely missing): set to date of previous sequential dosing “milestone” + 1

If (*year* is present and *month* and *day* are missing) or (*year* and *day* are present and *month* is missing): set to January 1st

If *year* and *month* are present and *day* is missing: set to the first day of the month

If the imputed date is before the previous sequential dosing “milestone”: set to the date of previous sequential dosing “milestone” + 1

### Incomplete Study Treatment Stop Date

Define next sequential dosing “milestone” as the earliest of next dose start date, next dose hold start date, date of last dose from EOT CRF or the cutoff date.

If *year* is missing (or completely missing): set to date of next sequential dosing “milestone” - 1

If (*year* is present and *month* and *day* are missing) or (*year* and *day* are present and *month* is missing): set to December 31st

If *year* and *month* are present and *day* is missing: set to the last day of the month

If the imputed date is after the next sequential dosing “milestone”: set to the date of next sequential dosing “milestone” - 1

## **Appendix B: Rounding Rules for Reported Percentages**

For percentages  $\geq 10\%$ :

- Values  $\geq X.5$  or above round to  $X+1$ .
- Values  $>X$  but  $<X.5$  round to  $X$ .

For percentages  $< 10\%$ :

- Values  $\geq X.Y5$  or above round to  $X.Y+0.1$ .
- Values  $>X.Y$  but  $<X.Y5$  round to  $X.Y$ .

## **Appendix C: Imputation Rules for Laboratory Values Outside of Quantification Range**

- Lab values below the lower level of quantification (LLQ) that are reported as “<LLQ” or “≤LLQ” in the database will be imputed by  $LLQ \times 0.99$  for analysis purposes. However the original value will also be maintained.
- Lab values above the upper level of quantification (ULQ) that are reported as “>ULQ” or “≥ULQ” in the database will be imputed by  $ULQ \times 1.01$  for analysis purposes. However the original value will also be maintained.

